14.1.4 Six Month Follow up (for all participants)

The six month follow up will take place at 6 months +/- 14days after the treatment date for patients in the ablation arm.

The six month follow up will take place at 6 months post randomisation +/- 14days in the active surveillance arm.

At the 6 month follow up the following will be administered to all patients:

- Blood test and urinalysis will be taken as per local policy. There is no requirement to report these to the study team or record them on the study eCRF.
- SF-36
- STAI
- FACT-G

For patients receiving active surveillance: data is to be captured from a routine follow up CT/MRI scan of the abdomen performed at 6 months after randomisation in order to document any changes in tumour progression.

For patients receiving an ablative procedure: data is to be captured from a routine follow up CT/MRI scan of the abdomen performed at 6 months after the procedure in order to document any changes in tumour progression.

The imaging will allow capture of the following data on the eCRF:

- Tumour size and volume. Size is to be recorded in 3 planes of measurement. Volume = $0.5236 \times (\text{diameter } 1) \times (\text{diameter } 2) \times (\text{diameter } 3)$. The volume calculation is not to be completed by site.
- Confirmation of any progression of the tumour.

The following additional data will also be captured for all patients:

- Any changes in treatment plan (eg switching from active surveillance to ablation or surgical excision). Dates and times and types of procedures to be recorded. Reasons for a switch in treatment (i.e. reason for cross-over).
- Complications of treatment and adverse events will be recorded.
- Administration of health economics questionnaire: PCQ (Part A and Part B)

14.1.5 Renal Biopsy (for any patients receiving ablation)

A routine, standard care biopsy will be performed post-consent as part of standard care prior to randomisation in study participants who have not already received this clinically. Should sites not perform this procedure as standard care, consent must be given by the participant to the procedure and the study prior to the biopsy.

A compulsory renal biopsy at the core of the ablated lesion will be performed on all patients who have received ablative treatment. This will normally take place within two weeks of the 6 month follow up visit. Results from the renal biopsies will be recorded in the trial eCRF.

Any further complications of treatment and adverse events will also be recorded at this time. The biopsy will be reported locally by a consultant urological pathologist (There may be an opportunity for central review). The biopsy report will contain the following information:

This data will be collected for biopsies at baseline and end of study

Lesional tissue present Y/N

Viable renal carcinoma tissue present Y/N

Renal carcinoma histological type and grade:

Type: (1) clear cell carcinoma, (2) papillary cell carcinoma type 1, (3) papillary cell carcinoma type 2, (4) chromoplata carcinoma; (5) oncocytoma; (6) can't determine

Grade: (1) Fuhrman grade 1/2, (2) Fuhrman grade 3/4, (3) can't determine

Presence of inflammation and/or sclerosis Y/N

Necrotic tumour present Y/N

The following data will be recorded at end of study biopsy only:

Biopsy outcomes

There will be three possible biopsy outcomes based on the histology and immunohistochemistry interpretation. Pathology should be reported locally as belonging to one of the biopsy outcome categories based on the biopsy protocol provided by [name] - Professor of Histopathology.

[figure not shown]
1. Failed biopsy
 - a. No tissue or non-renal tissue
 - b. Normal renal tissue
2. Fibrosis
 - a. Suggestive of ablation site (Inflammation, haemorrhage, haemosiderin)
 - b. Not suggestive of ablation site (Old fibrosis, no evidence of recent inflammation or haemorrhage)
 - c. Inconclusive
3. Renal tumour (Classify and grade)
 - a. Tumour cells with Ki67 reactivity
 - b. Tumour cells without Ki67 reactivity

Participating centres are to identify a Histopathologist at site that would be involved in the SURAB trial.

That pathologist should then contact [name] for guidance about interpretation of post ablation biopsies (contact details are in Section 1 of the protocol)

14.1.6 STUDY FLOW CHART

PILOT FEASIBILITY TRIAL

14.1.7 General information about Parallel Qualitative Component Data and Interviews

Interviews with patients and clinicians will be conducted by an experienced qualitative researcher with skills in interviewing vulnerable populations around sensitive topics and cognitive interviewing techniques. Interviews will be digitally recorded with the permission of the interviewees and transcribed verbatim. A topic guide will be developed from discussions with the wider team and from literature around trial participation. The topic guide will be used in the interviews but interviewees will be encouraged to speak freely about any other issues relating to the pilot feasibility trial. The guide will be revised as new issues emerge in each interview.

Transcript data will be managed using NVivo software. A thematic framework will be derived from the data through a process of data familiarization to look for emergent themes. This framework will be tested and refined and data will be coded using the final framework. Data will be analysed using the constant comparison method³⁹.

14.2 Data Handling & Record Keeping

Trial data collected on paper and any questionnaires will be entered on a secure validated clinical online data management system (MACRO database system). The MACRO database system will be managed by Newcastle Clinical Trials Unit.

Data will be handled, computerised and stored in accordance with the Data Protection Act 1998. Participants will be allocated a unique study identifier which will be used on all data report forms.

No participant identifiable data will leave the study site unless for the purposes of coordinating and undertaking qualitative interviews in which only the minimum data required will be used by the research team to facilitate contacting patients. Caldicott approval will also be sought from relevant NHS Trusts for patient identifiable information to leave study sites in order to enable the qualitative researcher to contact patients who express an interest in being contacted about the interviews.

The quality and retention of study data will be the responsibility of the Chief Investigator, [name]. All study data will be retained in accordance with the latest Directive on GCP (2005/28/EC) and local policy.

14.3 Submission of accrual data to UK CRN

This study will apply for adoption to the NIHR CRN Portfolio. Accrual data will be submitted on a monthly basis, by Newcastle Clinical Trials Unit, in accordance with NIHR CRN guidelines.

14.4 Schedule of Events

	Visit 1	Visit 2	Visit 3	Visit 4	Visit 5	Visit 6
Procedure	Screening	Baseline	Randomisation	Treatment (ablation)	Follow up 1	Follow up 2
			At least 24 hours after screening	1 month post randomisation (±14 days)	3 months post randomisation in active surveillance or 3 months post ablation (±14 days)	6 months post randomisation in active surveillance or 3 months post ablation (±14 days)
PIS provided	X					
ICF signed		X ²				
Patient randomised			X			
Eligibility criteria checked	X	X				
Medical History		X				
ASA physical status		X				
SF-36		X			X	X
STAI		X			X	X
FACT-G		X			X	X
CT/MRI scan³	X				X ⁴	X
Pre randomisation Biopsy		X ⁵				
Post ablation Biopsy						X ¹
Ablation (ablation arm only)				X		
Adverse Events				X	X	X
PCQ – Part A					X	X
PCQ – Part B						X
Sub Study Interviews		X ⁴				

¹ Ablation Arm Only

² Patient must be allowed at least 24hrs to review the patient information sheet prior to giving consent.

³ Scan of abdomen is required. CT is preferred method however MRI can be used instead of CT scan. The same scan technique must be performed throughout the study. Pre-screening CT/MRI is NOT a study procedure – performed as part of routine clinical care. Sites can perform additional scans if deemed clinically necessary/as per local practice.

⁴ Interviews conducted via telephone

⁵ Unless already performed as part of routine clinical care

^ can be taken up to 4 weeks prior to ablation.

^^ should be done within 3 months of ablative procedure – at a time that fits in with local practice. The 3 month scan is performed in the active surveillance arm if part of routine clinical care at site.

15. Economic Evaluation Protocol

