- Examine the mechanism of data collection and assess the completion rates of data collection instruments to inform the full trial.

9. Study Design

This is a multi-centre two arm trial which will evaluate the relative effectiveness between ablation and active surveillance in patients with small renal cancer (<4cm).

This is a pilot study and is not expected to produce definitive results but should provide a basis for planning a larger definitive trial on this topic.

9.1 Primary outcome measures:

The aim is to establish whether a future definitive trial comparing active surveillance with ablative treatment for small kidney cancer is feasible.

This will be assessed quantitatively in terms of recruitment and retention rates and qualitatively in terms of the patients' experiences and understanding of the randomisation process and treatment options.

Partition of reasons for loss to follow up, together with clinical data, will allow us to project likely retention at 5 years.

9.2 Secondary outcome measures:

All secondary outcomes will be rehearsed during the pilot trial with a view to refining the choice of outcomes for the main trial, based on data yield and quality.

Outcome data collection in the pilot feasibility trial will be timed to coincide with routine clinical assessments and will be collected from patients at 4,7 months post randomisation (3, 6 months post treatment).

The following secondary outcome questionnaires will be completed at baseline and at 3 and 6 months post treatment:

- a general health questionnaire (SF-36)
- cancer specific health status and quality of life (FACT-G)
- anxiety and depression (STAI)

We will also develop and test health economics data collection tools in the form of a participant costs questionnaire (PCQ). The PCQ has two parts: Part A to be administered at 3 month and 6 month and Part B at 6 month only.

9.3 Definition of end of study:

The end of study will be the last participant's final study contact, at their 6 month post treatment follow up.

10. Participants

Participants will be patients with renal cancer masses <4cm.

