12.1 Interventions being assessed

Patients recruited to the pilot feasibility trial who agree to be randomised to either ablation or active surveillance will undergo routine biopsy of the renal tumour to confirm that it is a cancerous growth. At centres where this biopsy is not routine, the participant must consent to the biopsy and the study prior to the biopsy being performed. Details of the biopsy can be seen in section 14.1.5 of the protocol.

Patients randomised to the ablation arm will undergo second compulsory biopsy six months after treatment. This will be conducted under ultrasound or CT guidance using local analgesia.

The ablation methods used will depend on what expertise is available at study sites. Sites will offer only one form of ablation. The permitted ablation methods will include Radiofrequency ablation (RFA), cryoablation (CRA) and microwave ablation (MWA).

The paragraphs below give more detail about the ablative procedures and active surveillance.

Radiofrequency ablation (RFA): Radiofrequency probes are carefully positioned into the renal mass lesion percutaneously by image guidance (usually using CT) and laparoscopically by direct vision.

RF probes deliver localized monopolar currents at 'radiofrequency' (400-500kHz) to generate frictional heating in the adjacent tissue. Through direct and conductive heating, this achieves temperatures of up to 105°C. Tissue destruction occurs by protein denaturation, cell destruction and coagulative necrosis in a sometimes ill-defined sphere around the probe tip. This ablation zone can be compromised by tissue perfusion-mediated cooling and larger adjacent flowing vessels but can usually achieve ablation zones of up to 4-5cm in diameter. Sometimes probes may be re-positioned to achieve the required ablation volume.

The procedure is well-tolerated but now more usually performed under general anaesthesia to achieve optimal probe positioning and outcomes. Where necessary, adjacent bowel or other structures are displaced by contrast-tinted 5% dextrose for retroperitoneal hydrodissection (however, carbon dioxide can also be used). Therapeutic outcomes are confirmed by contrast-enhanced CT or MR within 3 month post-ablation⁴⁰.

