14.1.3 Three Month Follow up (for all participants)

The three month follow up will take place at 3 months (+/-14days) after the treatment date for patients in the ablation arm.

The three month follow up will take place at 3 months post randomisation (+/-14days) in the active surveillance arm.

At the 3 month, follow up the following will be administered to all patients:

- Blood test and urinalysis will be taken as per local policy. There is no requirement to report these to the study team or record them on the study eCRF.
- SF-36
- STAI
- FACT-G

Imaging results will need to be obtained in order to document any changes in tumour progression as follows:

- For patients receiving ablation (using any of the methods) data is to be captured from a routine CT/MRI scan of the abdomen performed within 3 months of the ablative procedure
- For patients receiving active surveillance: a 3 month post randomisation scan of the abdomen is optional depending on routine practice at site.

The imaging will allow capture of the following data on the CRF:

- Tumour size and volume. Size is to be recorded in 3 planes of measurement. Size is to be recorded in 3 planes of measurement. $\text{Volume} = 0.5326 \times (\text{diameter } 1) \times (\text{diameter } 2) \times (\text{diameter } 3)$. The volume calculation is not to be completed by site.
- Confirmation of any progression of the tumour.

The following additional data will also be captured for all patients:

- Any changes in treatment plan (eg switching from active surveillance to ablation or surgical excision). Dates and times and types of procedures to be recorded. Reasons for a switch in treatment (i.e. reason for cross-over).
- Complications of treatment and adverse events will be recorded
- Administration of health economics questionnaire: PCQ (Part A)

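### The Schedule of Events times the ablation arm's final visit and compulsory biopsy at 3 months after ablation; the protocol text says 6 months.

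*Protocol*

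**What the plan says.** Section 14.4 sets out six visits. Visit 5 (first follow-up) is timed at "3 months post randomisation in active surveillance or 3 months post ablation (±14 days)" and Visit 6 (second follow-up) at "6 months post randomisation in active surveillance or 3 months post ablation (±14 days)". In the Visit 6 column the table marks the scan, SF-36, STAI, FACT-G, adverse events, the cost questionnaire (Parts A and B) and, for the ablation arm only, the row labelled "Post ablation Biopsy". That biopsy is marked nowhere else.

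The text gives a different time for the same events:

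- Section 14.1.4: "The six month follow up will take place at 6 months +/- 14days after the treatment date for patients in the ablation arm".
- Section 12.1: "Patients randomised to the ablation arm will undergo second compulsory biopsy six months after treatment".
- Section 14.1.5, on the biopsy of the ablated lesion: "This will normally take place within two weeks of the 6 month follow up visit".
- Section 9.2: the questionnaires are "completed at baseline and at 3 and 6 months post treatment".

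Section 9.3 ends the study at the last participant's contact 6 months after treatment. The Protocol Summary (section 6) places outcome collection at 4 and 7 months from randomisation, which it equates with 3 and 6 months from treatment.

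**The concern.** The ablation timing in the Visit 6 header repeats the Visit 5 timing, so an ablation patient's two follow-ups fall in one window with nothing between them. A visit schedule is normally the page a site uses to book appointments, and this one gives the wrong date for a compulsory invasive biopsy as well as for every final outcome.

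If a site followed the header:

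- The biopsy would be taken about 3 months early. Unless it were repeated, the biopsy part of the six-month persistence assessment would be lost for that patient. Rehearsing that assessment is the secondary objective in section 6.
- The 6-month questionnaires would be missing. Section 16.2 plans an interval estimate for the proportion of patients with outcomes at 3 and 6 months, and a retention criterion based on follow-up.
- Part A of the cost questionnaire, which section 15.4.2 spaces at 3-month intervals to limit recall bias, would be given twice in one window.
- Section 19.3 records serious adverse events up to the final follow-up or 6 months after treatment. Those two limits would no longer coincide in the ablation arm.

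**Working it through.** No power or sample-size figure is involved. The check compares the table with the text and converts both to time from randomisation.

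**Inputs**

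- Randomisation to ablation: 1 month ±14 days (sections 14.1.2 and 14.4).
- First ablation follow-up: 3 months after treatment. Section 14.4 and section 14.1.3 agree: "The three month follow up will take place at 3 months (+/-14days) after the treatment date for patients in the ablation arm".
- Second ablation follow-up: 3 months after treatment in section 14.4; 6 months in section 14.1.4.
- Surveillance follow-ups: 3 and 6 months from randomisation (sections 14.1.3, 14.1.4 and 14.4 agree).
- Planned ablation arm: 30 patients (section 16.1).

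**Formula for the ablation arm:** months from randomisation = 1 + months from ablation.

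| | Table as printed (14.4) | Text (14.1.3, 14.1.4) |
|---|---|---|
| Ablation, first follow-up | 1 + 3 = 4 months | 1 + 3 = 4 months |
| Ablation, second follow-up and biopsy | 1 + 3 = 4 months | 1 + 6 = 7 months |
| Interval between the two | 4 − 4 = 0 months | 7 − 4 = 3 months |
| Surveillance, second follow-up | 6 months | 6 months |

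The text column reproduces the 4 and 7 months given in section 6 and section 9.2. The table column does not.

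**Can the visit window absorb the difference?** No. A visit at the late end of the 3-month window and one at the early end of the 6-month window together use 14 + 14 = 28 days, about one month of a three-month gap. Adding the two weeks that section 14.1.5 allows around the visit for the biopsy gives 28 + 14 = 42 days, still well short.

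**Does any other section support 3 months?** None does. Sections 6, 9.2, 9.3, 12.1, 12.2, 12.3, 14.1.4, 14.1.5, 15.4.1 and 15.4.2 all place the final ablation assessment, or some part of it, at 6 months.

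**The case against.** The strongest reply is that this is one wrong digit that gives itself away. Visits 5 and 6 cannot sensibly be the same visit, the surveillance timings in the same two columns read 3 and 6 months, and the rest of the protocol agrees on 6. The intended timing is not in doubt. Section 18.2 also provides for training at investigator meetings and site initiation, monitoring visits, and central review of outstanding data, all of which make an unnoticed early biopsy less likely. A patient seen early could still have the routine 6-month scan. The recruitment criterion (at least 49 of 120 approached) is unaffected, and persistence of cancer is a secondary outcome in a feasibility trial.

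Most of this stands. It is an internal inconsistency, not a design the trial chose. Nothing in the protocol shows that any site followed the header, and 30 patients is a ceiling, not an estimate of how many were affected. But these points bear on how likely harm is, not on whether the table is right. The protocol does not say whether the table or the text prevails. Seeing that two columns duplicate each other also does not tell a coordinator which entry is wrong unless they go back to the text.

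**Conclusion.** The concern holds. As printed, the Visit 6 ablation timing is 3 months too early and contradicts every other section that times the same events. It merges the two ablation follow-ups at about 4 months from randomisation, where the text has 4 and 7. The most it could affect is the final assessment of all 30 planned ablation patients. The actual effect depends on whether any site used the header, which the protocol cannot show. The conversion to time from randomisation assumes ablation at the planned 1 month. The contradiction itself, which is stated in time from ablation, needs no such assumption. Sample size and the recruitment criterion are unaffected. Because the entry governs an invasive procedure and the final outcomes, it should be corrected and not left for readers to work out.

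**What to change.** In section 14.4, change the ablation part of the Visit 6 header from 3 to 6 months post ablation, keeping the ±14 days. The final ablation visit then falls at about 1 + 6 = 7 months from randomisation, in line with sections 6 and 9.2, and matches sections 12.1, 14.1.4 and 14.1.5. Reissue the table to sites with a short notice. For ablation patients already treated, compare the actual dates of second follow-up and biopsy with the 6-month window, and record any that were early because of the table as deviations.

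The cost is one table entry, a minor amendment, a notice to sites and a check of dates for at most 30 patients. No analysis or sample-size change follows.

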15.1 Aim

The pilot study aims to assess the feasibility of a definitive randomised controlled trial (RCT) comparing ablation with active surveillance for treating small renal tumours. The economic aspect of the pilot will develop and test the health economics data collection tool and assess the ease of data collection required for health economic analysis to inform the definitive trial. The study will adopt the view point of both the NHS and the patient, and collect resource use data which include the costs of treatments and the use of primary and secondary NHS services, as well as participants' out-of-pocket expenses relating to the condition.

15.2 Collecting data

Tables detailing data to be collected and their source are provided in Appendix 1. Dummy tables for response rates, resource use, unit cost, average cost for each trial arm are designed (Appendix 2), and will be populated with data collected through the trial.

15.3 Outcomes

Quality of life (QoL) outcome data will be collected through the administration of the SF-36 questionnaire, which will be completed by participants at 3 and 6 month follow-up. The completeness of the questionnaire will be assessed.

15.4 Costs

15.4.1 Intervention cost

The main cost driver of treating patients with small renal tumour is expected to originate from the intervention (ablation treatments): Cryoablation, Microwave and Radiofrequency ablation (RFA). The key cost components include staff, consumables, capital and overheads. Data on these costs will be obtained from participating centres. The following information to be used to derive resource use will be recorded in the Case Report Form (CRF) for each participant in the ablation arms of the trial:

- Type of anaesthetic used (general or local)
- Grade of anaesthetist present
- Grade of radiologist present
- Grade of assistant staff present
- Number of nursing & assistant staff present
- Time of patient entry and exit from CT Suite
- Time of patient entry and exit from recovery room
- Date of admission
- Date of discharge
- Post-treatment complications (Clavien- Dindo grade if applicable)

The unit costs of each item will be obtained from the following sources: the costs of consumables and reusable items used during the procedure will be derived from manufacturers' price lists; the standard time costs of different grades of staff will be obtained through Unit Cost of Health and Social Care documentation from Personal Social Services Research Unit (PSSRU)⁴²; cost per unit of time for CT suite will be based upon data from each participating centre. In the event of a complication the cost can be obtained from the participating centre based on the grade of complication defined by the Clavien-Dindo⁴³.

Participants in both of the study arms will be offered CT and/or MRI scans to monitor small renal tumour progression. For patients receiving ablation (using any of the methods) data is to be captured from two routine CT/MRI scans performed within 3 and 6 months of the ablative procedure. For patients receiving active surveillance: data is to be captured from two routine follow up CT/MRI scans performed within 3 and 6 months from randomisation. The unit cost per scan will be obtained from participating centres.

